## 10.2 Safety Review

Both the risks listed in Section 4.1 and unknown risks will be monitored as follows:

### **Safety monitoring**

The Principal Investigator will be responsible for ensuring that adverse events are reported to the local Institutional Review Board in compliance with requirements. Any changes to the protocol will be made in accordance with local IRB policies. The Principal Investigator will supervise all study activities, including those of the research coordinators and co-investigators, and will be available 24 hours by page. The physician investigators will review all laboratory results and adverse events.

General safeguards will be in place for all subjects enrolled in the study. All subjects will have access to 24 hours a day, 7 days a week coverage provided by the PI or designated substitute by pager for emergencies. The PI will be responsible for monitoring the safety of the study and complying with the reporting requirements. Continuous, close monitoring of participant safety will include prompt and frequent reporting of safety data (i.e., adverse/serious adverse events) to the Boston Medical Center Institutional Review Board and/or appropriate study staff with oversight responsibility. Serious adverse events and unanticipated problems will be reviewed by the PI within 24 hours of the study team knowing about the AE/UP. Unanticipated Problems (UPs) will be reported to the Data Safety and Monitoring Board (DSMB) chair within 24 hours of the PI learning of the event and to the IRB within 7 days. Non-serious adverse events will be reviewed by the PI within 7 days of a study visit. A summary of serious adverse events and AEs will be reviewed by the PI every 6 months during progress reports as well as during the written report required by the IRB as part of the annual IRB renewal process.

### **Data Safety and Monitoring Board (DSMB)**

We have established a DSMB board which includes the following members:

- [name] M.D.; Child Psychiatrist, Researcher; Massachusetts General Hospital
- [name] M.D.; Child Psychiatrist, Researcher; Massachusetts General Hospital
- [name] Ph.D.; Child and Addiction Psychologist, Addictionologist, member of the MGH QI/QA committee; Massachusetts General Hospital
- [name] M.P.H.; Statistician; Massachusetts Department of Public Health, and Massachusetts General Hospital

The DSMB will meet once per year during the active study and most recently met on 09/10/2019. The DSMB will be provided with unblinded data from the study so as to examine whether the study should be stopped because the drug interventions are either clearly beneficial or harmful to participants. In addition to the IRB, the K12 PI, and the NIH project officer, the DSMB chair will be informed of any unanticipated problems that occur during the trial. The primary concern of the investigators of this study is the safety of the subjects.

**Adverse Event Reporting:** Consistent with good clinical practice, safety will be monitored by study staff at each study visit. A study clinician will supervise all study activities including ratings, reported adverse events, lab results and vital signs, and the Principal Investigator, [name], will be available for further review. Should any study activities require urgent attention, the PI and study clinicians will be available 24 hours a day by page. All procedures have been designed to minimize subject discomfort, and no subject will be asked to engage in research procedures not outlined in the consent form. Subjects will be monitored for adverse events at each visit. All adverse events (including unexpected and serious AEs) will be recorded and reported in accordance with Boston Medical Center Institutional Review Board guidelines. We will follow and adhere to all guidelines as defined and outlined on the Boston Medical Center Institutional Review Board website:

[http://www.bumc.bu.edu/irb/files/2019/06/Reporting\\_Requirements.pdf](http://www.bumc.bu.edu/irb/files/2019/06/Reporting_Requirements.pdf)

### **Data Monitoring**

The PI will be responsible for ongoing quality control. This includes all aspects of the study related to safety, but also data integrity and protocol compliance. Quality control will include self-audits of data collection and storage as well as compliance with the informed consent procedure. The review of data and procedures may result in early termination of the study, amendment of the protocol or data collection plans, or amendment of study forms. The IRB will be notified and all amendments approved prior to study implementation. In addition, the participants will be notified of any significant new findings that develop during the course of research (e.g., other potential risks) that may affect their wish to continue participation in the study.

The study clinicians, research coordinator, and Principal Investigator will monitor study progress including enrollment, adherence to inclusion/exclusion criteria and study protocol, as well as any adverse events. The Principal Investigator will be responsible for ensuring that adverse events are reported to the local Institutional Review Board in compliance with local and federal requirements. Any changes to the protocol will be made in accordance with local IRB policies. The Principal Investigator will supervise all study activities, including those of the research coordinator and co-investigators, and will be available 24 hours a day by page.

For quality control purposes, audio of clinician-administered measures completed during the visits may be recorded, with subjects' permission. These recordings will be used to monitor quality control and inter-rater reliability in this study by the PI. Each audio file will be coded with subject initials and number to maintain confidentiality. These recordings will be de-identified and stored in a password-protected file.

### **10.3 Reporting Plans**

The Principal Investigator at BMC/BU Medical Campus will report Unanticipated Problems, safety monitors' reports, and Adverse Events to the BMC/BU Medical Center IRB in accordance with IRB policies:

- Unanticipated Problems occurring at BMC/BU Medical Campus will be reported to the IRB within 7 days of the investigator learning of the event.
- Reports from safety monitors with recommended changes will be reported to the IRB within 7 days of the investigator receiving the report.
- Adverse Events (including Serious Adverse Events) will be reported in summary at the time of continuing review, along with a statement that the pattern of adverse events, in total, does not suggest that the research places subjects or others at a greater risk of harm than was previously known.
- Reports from safety monitors with no recommended changes will be reported to the IRB at the time of continuing review.

### **10.4 Stopping Rules**

A subject will be withdrawn from the study if they:

- Develop an adverse event despite dose adjustments that is determined to be intolerable based on clinician judgment. An intolerable event is any side effect or worsening of SMD or SUD symptoms that are determined by the investigator to be excessive in severity or in duration
- Have worsening SMD or SUD symptoms (as determined by clinician judgment indicated through scores  $\geq 5$  on the CGI Global Improvement scale on two consecutive weeks) that warrants an early termination
- Have new onset of severe SUD (e.g. intravenous, intentional/unintentional overdose)
- Have unstable mental health (new onset SI/HI with intent and/or plan)
- Become incarcerated
- Demonstrate severe noncompliance with medication dosing or study procedures
- Become pregnant during the study
- Modify their psychiatric and/or non-psychiatric medications such that they would be increasing the dose of an existing medication that may prolong QTc interval
- Add a new medication that may prolong QTc interval
- Gain weight such that their BMI increases by  $\geq 1$  point if 1) their starting BMI is between 30-35 or 2) their starting BMI is  $< 30$  but BMI at midpoint is between 30-35

In case of an emergency, the investigator will be able to contact the Boston Medical Center research pharmacy for emergency unblinding 24 hours a day. The blinded information is to be broken only when knowledge of such treatment may have an impact on future treatment decisions or aid in the emergency treatment of the subject. This decision can only be made by [name] or designee. Any subject for whom the blind is broken will be discontinued from the study. If an SAE occurs, the principal investigator, [name] or designee, should be informed of the event within 24 hours so appropriate actions may be taken.

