Subjects will be given quetiapine throughout the study. The most frequently observed adverse reactions (incidence  $\geq$  5% and twice placebo) associated with the use of quetiapine include: somnolence, dry mouth, dizziness, pharyngitis, weight gain, constipation, lethargy, ALT increase, postural hypotension, hypertension, dyspepsia, fatigue, increased appetite, tachycardia, vomiting and asthenia. Serious adverse reactions associated with the use of quetiapine include: hyperglycemia, lipid elevations, hypothyroidism, neuroleptic malignant syndrome, seizures, diabetes mellitus, cataracts, QTc prolongation, and tardive dyskinesia. Tardive dyskinesia causes repetitive involuntary movements. The movements most commonly appear in the eyes, lips, tongue, and jaw. Although tardive dyskinesia is rare it can be irreversible.

To minimize adverse reactions a baseline EKG will be completed to assess QTc length, and subject's past medical history will be assessed for thyroid dysfunction, seizures, diabetes mellitus, and cataracts. Adverse reactions will be monitored during the study by assessing for adverse events, as well as vital signs including blood pressure, heart rate, and weight, blood testing (lipids, glucose, AST, ALT), and extrapyramidal symptoms including tardive dyskinesia (AIMS).

Problems and side effects not listed above and not known at this time could occur. Subjects will be told of any changes in the way the study will be done and any newly discovered risks to which they may be exposed.

Quetiapine has a black box warning for increased suicidality risk in adolescents and young adults largely due to co-administration in patients with major depressive disorder who are on antidepressants.

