## 11.2 Source Documents

Structured diagnostic and psychosocial interviews will be collected from youth and parents when available. Biological samples of blood will be collected to measure hepatic function, test for hepatitis C and HIV, and monitor glucose and lipid levels during treatment. Urine samples will be collected to measure drug toxicology and detect pregnancy. For a full list of data records, please see the Schedule of Events in the Appendix.

Data generated by the methods described in the protocol will be recorded in the subjects' medical records and/or special research files, one per subjects, which will be identified by an ID number that will not identify the subject in any way. Data may be transcribed legibly on hard copy CRFs supplied for each subject or directly inputted into REDCap—an electronic data management system. Any hard copy material including the names of subjects or other identifying information (consent/assent forms, paper records) will be kept in locked filing cabinets in a locked room or scanned and uploaded to a password-encrypted folder on the BMC secure network. Documentation linking subjects' names and numbers will be kept in a password-protected electronic file on a BMC networked drive only accessible by the project coordinator and primary investigator (PI) on a password-protected computer located behind a secure and maintained firewall. Blood sample collection, analysis and disposal will be managed by the BMC lab. Urine sample collection, analysis, and disposal will be managed by study staff and samples will not contain identifying information. Data will be transmitted only in pooled form, and subjects will be identified by ID numbers. Any publications of study findings will be reported so that no person can be identified individually. These issues will be clearly stated in consent forms and discussed with participants during the informed consent process, prior to any study related procedures.

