## 11.3 Case Report Forms

The study case report forms (CRF) will be the primary data collection instruments for the study. All data requested on the CRFs will be recorded. All missing data will be explained. If a space on the CRF is left blank because the procedure was not done or the question was not asked, "N/D" will be written. If the item is not applicable to the individual case, "N/A" will be written. All entries will be printed legibly in black ink. If any entry error has been made, to correct such an error, a single straight line will be drawn through the incorrect entry and the correct data will be entered above it. All such changes will be

initialed and dated. There will be no erasures or white-out on CRFs. For clarification of illegible or uncertain entries, the clarification will be printed above the item, then initialed and dated.

See the Appendix for the following CRFs:

Clinician rated assessments (stored in patient files/ REDCap):

- Mini-International Neuropsychiatric Interview (M.I.N.I. 7.0)
- DMS-V Kiddie Schedule for Affective Disorders and Schizophrenia Present and Lifetime (KSADS-PL) module for DMDD
- Weiss Adherence Interview
- Adverse Experiences and Concomitant Medications
- Young Mania Rating Scale (YMRS)
- Abnormal Involuntary Movement Scale (AIMS)
- Clinical Global Impressions (CGI)[62] scale for SUD and SMD
- Columbia Suicide Severity Rating Scale (C-SSRS)
- DSM-V Global Assessment of Functioning (GAF) scale
- Reproductive Potential Form

Subject/Parent rated scales (stored in patient files/REDCap):

- Socioeconomic Status/Background
- Youth Self-Report (YSR) and Adult Self-Report (ASR)
- Behavior Rating Inventory of Executive Function (BRIEF)
- Beck Depression Inventory-II (BDI-II)
- Patient Health Questionnaire-9 (PHQ-9)
- Weiss Craving Scale
- Fagerström Tolerance Questionnaire for Adolescents
- Timeline Followback of Substance Use (TLFB)
- Risk Behavior Survey
- Supplemental Substance Use Questionnaire

Other CRFs (stored in patient files/REDCap):

- Laboratory tests: Drug screen (urine and breathalyzer), Urine HCG

- Safety/reliability procedures: EKG, Heart Rate, Blood Pressure, Height, Weight
- Chart Note
- Adverse Events Log
- Concomitant Medication Log
- COVID-19 Screening Questions

Other CRFs stored in patient Medical Record and patient files/REDCap

- Laboratory tests: AST/ALT, Hepatitis C, HIV, Fasting Lipids, Fasting Glucose, Urine THC, Creatinine

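### Outcome-linked withdrawal ends study participation, and the planned unweighted GEE has no safeguard, so the drug effect may be modestly understated

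*Combined protocol and SAP*

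**What the plan says.** All references are to the combined protocol and SAP.

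- **Exit is from the study.** The list in 10.4 opens "A subject will be withdrawn from the study if they".
- **Several reasons are the outcomes themselves.** Besides the CGI rule ("Have worsening SMD or SUD symptoms (as determined by clinician judgment indicated through scores"), the list has "Have new onset of severe SUD" and new suicidal or homicidal ideation with intent or plan. It also has intolerable events, defined thus: "An intolerable event is any side effect or worsening of SMD or SUD symptoms".
- **Other reasons may be drug-related.** Intolerable side effects are covered by the same definition. A further reason begins "Gain weight such that their BMI increases by" and applies to a rise of 1 point or more in subjects whose BMI is 30-35 at the start or at midpoint. Section 6.1 lists common reactions "associated with the use of quetiapine include: somnolence, dry mouth, dizziness, pharyngitis, weight gain".
- **After exit.** Section 6.1 offers up to three clinical follow-up visits, and the offer of quetiapine after the study appears to reach early withdrawals. Section 9.4 mentions a drop visit in a sentence on safety measures. Neither section names TLFB, craving, YMRS or BDI-II after withdrawal. Section 11.2 says "For a full list of data records, please see the Schedule of Events in the Appendix"; that schedule was not supplied.
- **Analysis.** Section 12.3 uses GEE with drug, time and their interaction in a modified ITT set. It names no working correlation, weights, missingness assumption or sensitivity analysis. TLFB, first in the SUD hierarchy, compares the month before entry with the last month of the study. The sentence in 11.3, "All missing data will be explained", is a rule for completing case report forms.

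**The concern.** A subject who deteriorates can be taken out because of the deterioration, and the later weeks are then absent from the analysis. If quetiapine works, this should happen more often on placebo. The placebo subjects who remain look better than the arm as randomized, and the difference shrinks. A subject withdrawn by about Week 4 contributes nothing to the last-month TLFB window. The allowance for 20% attrition in 12.2 restores precision but does nothing about selective loss. No planned analysis would show how much the result depends on who left.

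**Working it through.** **The plan's own figure.** Section 12.2 gives 22 per group for 90% power, two-sided 5%, and cites an effect size of about 1.0. The formula 2 × (z₀.₉₇₅ + z₀.₉₀)² / d² gives 2 × (1.95996 + 1.28155)² / 1.0² = 21.01, rounded up to 22. The t-test version gives 22.02. With 20% attrition, 22 / 0.8 = 27.5, so 28 per group and 56 in total. The sample size reproduces. Attrition of 20% is 0.20 × 56 = about 11 subjects.

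**Inputs for the bias.** The documents give no SDs and no withdrawal rates by reason, so everything below is assumed.
- Weekly use days = 5 + b0 + (slope + b1) × week + e. SD of b0 is 1; SD of e is 1 (0.5 at baseline); placebo slope is 0.
- Exit has probability 0.6 after two consecutive weeks above a threshold tuned to the placebo exit rate, at Weeks 2-7. Random loss is 0.6-1.3% per week. Total attrition is 16-22%.
- 20,000 per arm, six replicates. Loss % = 100 × (1 - estimate / estimate without dropout); a minus sign means overstated.

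**Check of scale.** With slope -0.125 the true last-month effect is -0.125 × (5 + 6 + 7 + 8) = -3.25 days in 28 (simulated -3.24). With SD b1 = 0.2, the SD of change is √((26 × 0.2)² + 4 × 1² + (4 × 0.5)²) = √35.04 = 5.92, so d = 3.25 / 5.92 = 0.55. At 28 per arm the sampling SD is 5.92 × √(2/28) = 1.58 days.

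**Loss (%) from worsening exits, about 13% on placebo**

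| Inputs | d | Two-period | Exchangeable GEE | Independence GEE | Mixed model |
|---|---|---|---|---|---|
| slope -0.125, SD b1 0.20 (exits 13.2% v 6.0%) | 0.55 | 6.1 | 5.7 to 7.5 | 9.9 to 12.8 | 0.1 to 0.2 |
| slope -0.125, SD b1 0.10 | 0.84 | 2.4 | 0.9 to 1.4 | 3.7 to 4.9 | -0.9 |
| slope -0.125, SD b1 0.062 | 0.99 | 1.1 | -0.9 to -0.8 | 1.6 to 2.1 | -1.6 to -1.4 |
| slope -0.227, SD b1 0.20 | 0.99 | 5.0 | 4.7 to 6.2 | 8.2 to 10.6 | 0.0 to 0.1 |
| rows 1 and 4, exit on a noisy rating of underlying course (noise SD 0.5-1.0) | 0.55, 0.99 | 5.3 to 9.1 | 5 to 10.8 | 7 to 14 | 3.4 to 6.0 |

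In rows 1-4 exit depends on the observed use days. Row 5 is closer to 10.4, where a clinician's CGI triggers exit. Heavier cases (20.2% placebo exits, or more variable courses) reach 9%, 12% and 18% for the first three analyses. With no drug effect and equal exits, all analyses stay within 0.006 days of the full-data result.

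**Against sampling error.** In row 1 the two-period loss is 0.061 × 3.24 = 0.20 days, and 9.1% would be 0.29 days. In 700 simulated trials of 28 per arm with row 1 inputs, the SDs were 1.59 (two-period), 1.54 (exchangeable), 1.56 (independence) and 1.61 (mixed).

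**Side-effect exits added to row 1.** If unrelated to course (10.9% quetiapine v 1.7% placebo), the two-period loss is 6.2%, almost unchanged. If confined to poor courses (10.3% v 1.6%), the two-period and exchangeable analyses overstate by 3-4% and the mixed model by 7-8%. With no drug effect, that pattern gives a false benefit of 0.24-0.39 days.

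**Counting use after worsening exits.** With the unrelated side-effect exits this gives -3.19 days (full data -3.22). With the poor-course exits it gives -3.43 (full data -3.22). For toxicology, the ratio of negative screens in row 1 is 1.41 in full data, 1.36 as observed and 1.44 with missing screens counted positive. The rule overshoots, so it is a bound.

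**The case against.** The strongest reply is that the bias is small and the remedy imperfect. Much of this stands.

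- **Size.** At the plan's effect size and with exit on observed use, the two-period comparison loses only 1-5%. From the 700 trials, root mean squared error is √(1.54² + 0.117²) = 1.544 for exchangeable GEE and √(1.61² + 0.073²) = 1.612 for the mixed model. The case for the mixed model is lower bias from worsening exits, not lower total error.
- **The mixed model is not a cure.** Its near-zero loss in rows 1-4 follows from triggering exit on the very data it models. Row 5 removes that advantage and leaves about 3-6%.
- **Endpoint.** Section 4.2.1 schedules the AIMS at baseline and endpoint, and 9.4 explains endpoint for that assessment as the completion or drop visit. Section 4.2.1 uses the same word for the efficacy scales, so the natural reading includes the drop visit. This needs confirming; it is not a gap. An exit-day value still says nothing about later weeks.
- **Unsupplied appendices.** The Schedule of Events or Data Management Plan may provide for later collection. A reader might infer that none is planned. The documents support only that none is stated in the supplied text. Section 12.3 would still lack a missing-data method.

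A reader might also infer that the bias is equally likely to favour the drug. That needs quetiapine subjects on a poor course to leave selectively for side effects, and the documents give no figure for this.

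**Conclusion.** The plan should be amended, as an improvement rather than a correction of a fatal flaw. Exit for worsening is written into 10.4, and 12.3 pairs it with a method that in general needs data missing completely at random. The likely direction, if the drug works and worsening exits are commoner on placebo, is understatement: roughly 1-9% for the two-period or exchangeable analysis (exchangeable up to about 11% in the least favourable run) and up to about 14% for independence GEE.

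These sizes rest on assumed variances, an assumed placebo worsening-exit rate of about 13% and an assumed trigger. They show order of magnitude only. No specific loss of power can be derived from the documents, and the stated sample size is not in error. Nor does the worsening rule alone create a false benefit: when exits are equal and there is no effect, bias is about zero.

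**What to change.** Leave the clinical withdrawal criteria unchanged.

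1. **Collection and estimand.** Separate stopping study medication from ending data collection. Where consent and contact allow, collect TLFB and the rating scales to Week 8 by phone or Zoom; 5.1 already permits scales by phone and 9.3 already has weekly TLFB. Record any open-label quetiapine taken after withdrawal. State the estimand, including whether data after such use enter the primary analysis. Only this item addresses side-effect exits directly.
2. **Primary model.** For the continuous outcomes, replace unweighted GEE with a likelihood-based repeated-measures mixed model using all observed visits. Model weekly TLFB and take the last-month contrast from it. A random intercept and slope is practical there, since an unstructured covariance over nine occasions needs 9 × 10 / 2 = 45 parameters. Craving, YMRS and BDI-II at Weeks 0, 2, 4, 6 and 8 need 5 × 6 / 2 = 15. This reduces bias from worsening exits and does not correct side-effect exits. Toxicology can stay with GEE.
3. **Sensitivity.** Repeat TLFB and toxicology counting days or screens after withdrawal for worsening as use or positive. Report this as a bound, not a correction.
4. **Endpoint.** Confirm that it includes the completion or drop visit for the efficacy measures.

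**Cost.** Items 2-4 need an analysis-plan amendment before unblinding and a slightly larger SD (1.61 v 1.54-1.59 days); the mixed model never failed in the 700 trials. Item 1 needs a protocol and consent amendment and contact with at most about 11 of 56 subjects, some unreachable. The 19 subjects randomized at the first site gain only from items 2-4.
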